### **8.4 Warnings and precautions**

No evidence available at the time of the approval of this study protocol indicated that special warnings or precautions were appropriate, other than those noted in the provided [Investigator Brochure]. Additional safety information collected between IB updates will be communicated in the form of Investigator Notifications. This information will be included in the patient informed consent and should be discussed with the patient during the study as needed.

## **8.5 Data Monitoring Committee**

An Independent Data Monitoring Committee (IDMC) will not be formed for this open-label phase II study. Individual patient data will be reviewed on an ongoing basis and aggregate safety data and the primary endpoint will be monitored quarterly by the study team across the duration of the trial based on the available data in the clinical database.

The data will be discussed with investigators in teleconferences, if deemed needed by the Novartis team. In case of having sufficient evidence of lack of efficacy for the study drug, Novartis and the investigator parties must reach a consensus on whether to terminate further patient enrolment in the treatment group.

## **8.6 Steering Committee**

A Steering Committee constituted of members of the Translational Clinical Oncology Leadership Team will be formed for this study. If the monitoring of the study data requires a decision to be taken on the continuation of the study, then the relevant data (e.g., safety data or primary analysis and predictive probability of success (PPOS)) will be communicated to the Steering Committee for decision making purposes.

# **9 Data collection and management**

## **9.1 Data confidentiality**

Information about study patients will be kept confidential and managed under the applicable laws and regulations. Those regulations require a signed patient authorization informing the patient of the following:

- What protected health information (PHI) will be collected from patients in this study
- Who will have access to that information and why
- Who will use or disclose that information
- The rights of a research patient to revoke their authorization for use of their PHI.

In the event that a patient revokes authorization to collect or use PHI, the investigator, by regulation, retains the ability to use all information collected prior to the revocation of patient authorization. For patients that have revoked authorization to collect or use PHI, attempts should be made to obtain permission to collect follow-up safety information (e.g. has the patient experienced any new or worsened AEs) at the end of their scheduled study period.

The data collection system for this study uses built-in security features to encrypt all data for transmission in both directions, preventing unauthorized access to confidential participant information. Access to the system will be controlled by a sequence of individually assigned user identification codes and passwords, made available only to authorized personnel who have completed prerequisite training.

Prior to entering key sensitive personally identifiable information (Patient Initials and exact Date of Birth), the system will prompt site to verify that this data is allowed to be collected. If the site indicates that country rules or ethics committee standards do not permit collection of these items, the system will not solicit Patient Initials. Year of birth will be solicited (in the

place of exact date of birth) to establish that the patient satisfies protocol age requirements and to enable appropriate age-related normal ranges to be used in assessing laboratory test results.

## **9.2 Site monitoring**

Before study initiation, at a site initiation visit or at an investigator's meeting, Novartis personnel (or designated CRO) will review the protocol and eCRFs with the investigators and their staff. During the study, the field monitor will visit the site regularly to check the completeness of patient records, the accuracy of entries on the eCRFs, the adherence to the protocol to Good Clinical Practice, the progress of enrollment, and to ensure that study treatment is being stored, administered, and accounted for according to specifications. Key study personnel must be available to assist the field monitor during these visits.

The investigator must maintain source documents for each patient in the study, consisting of case and visit notes (hospital or clinic medical records) containing demographic and medical information, laboratory data, electrocardiograms, and the results of any other tests or assessments. All information recorded on eCRFs must be traceable to source documents in the patient's file. The investigator must also keep the original signed informed consent form (a signed copy is given to the patient).

The investigator must give the monitor access to all relevant source documents to confirm their consistency with the eCRF entries. Novartis monitoring standards require full verification for the presence of informed consent, adherence to the inclusion/exclusion criteria and documentation of SAEs. Additional checks of the consistency of the source data with the eCRFs are performed according to the study-specific monitoring plan.

## **9.3 Data collection**

For studies using Electronic Data Capture (EDC), the designated investigator staff will enter the data required by the protocol into the Electronic Case Report Forms (eCRF). The eCRFs have been built using fully validated secure web-enabled software that conforms to 21 CFR Part 11 requirements. Investigator site staff will not be given access to the EDC system until they have been trained. Automatic validation programs check for data discrepancies in the eCRFs allow modification or verification of the entered data by the investigator staff.

The Principal Investigator is responsible for assuring that the data entered into eCRF is complete, accurate, and that entry and updates are performed in a timely manner.

PK and biomarker (blood, serum, plasma and/or tissue) samples obtained during the course of the study will be collected from the Investigator sites and analyzed by a Novartis designated laboratory, contracted central laboratories, or local laboratories. ECG data collected during the study will be reviewed and processed centrally by a specialist CRO. During the course of the study, Novartis may decide to have a central review of the radiological assessments performed. In such case, the investigator's staff will be instructed on how to send data from these radiological assessments to a Contract Research Organization (CRO) for central review when needed. Designated investigational site staff will enter the information required by the protocol into the appropriate eCRF and/or designated laboratory requisition forms. Field monitors will review the eCRFs and laboratory paper requisition forms for accuracy and completeness and instruct site personnel to make any required corrections or additions. One copy of the requisition

form will be forwarded to each analytical laboratory with the respective sample(s) by the field monitor or by the designated investigational site staff; and one copy will be retained at the investigational site.

#### **9.4 Database management and quality control**

For studies using eCRFs, Novartis personnel (or designated CRO) will review the data entered by investigational staff for completeness and accuracy. Electronic data queries stating the nature of the problem and requesting clarification will be created for discrepancies and missing values and sent to the investigational site via the EDC system. Designated investigator site staff is required to respond promptly to queries and to make any necessary changes to the data.

Concomitant treatments and prior medications entered into the database will be coded using the WHO Drug Reference List, which employs the Anatomical Therapeutic Chemical classification system. Medical history/current medical conditions and adverse events will be coded using the Medical dictionary for regulatory activities (MedDRA) terminology.

Samples and/or data will be processed centrally and the results will be sent electronically to Novartis (or a designated CRO).

For EDC studies, after database lock, the investigator will receive a CD-ROM or paper copies of the patient data for archiving at the investigational site.

### **10 Statistical methods and data analysis**

Data will be analyzed by Novartis and/or designated CRO. Any data analysis carried out independently by the investigator must be submitted to Novartis before publication or presentation.

It is planned that the data from participating centers in this protocol will be combined, so that an adequate number of patients will be available for analysis. Data will be summarized with respect to demographic and screening/baseline characteristics, efficacy and safety observations and measurements and all relevant PK and PD measurements using descriptive statistics (quantitative data) and contingency tables (qualitative data).

The primary analysis of PFS will be performed for the comparison of PDR001 with the control arm. The cutoff date for the primary analysis is after approximately 70 PFS events have occurred across both of the two arms combined (approximately 114 patients randomized). This analysis will include the primary and selected secondary endpoints of the study, as defined in the RAP.

The following rules will be followed for reporting results unless stated otherwise: data will be summarized and listed by study arm. Categorical data will be presented as frequencies and percentages. For continuous data, mean, standard deviation, median, minimum, and maximum will be presented.

Screen failure patients are those who signed the informed consent, but never started the study treatment for any reason. For these patients, the eCRF data collected, [Section 7.1.1](#), will not be included in any analysis, but will be reported in the CSR as separate listings.

The reason for discontinuation from study will be summarized and listed, along with dates of first and last study drug treatment, duration of exposure to study drug treatment and date of discontinuation for each patient. Other missing data will simply be noted as missing on appropriate tables/listings.

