## **6.4 Patient numbering, treatment assignment or randomization**

### **6.4.1 Patient numbering**

Each patient is identified in the study by a Patient Number (Patient No.), that is assigned when the patient is first enrolled for screening/baseline and is retained as the primary identifier for the patient throughout his/her entire participation in the trial. The Patient No. consists of the Center Number (Center No.) (as assigned by Novartis to the investigative site) with a sequential patient number suffixed to it, so that each patient is numbered uniquely across the entire database. Upon signing the informed consent form, the patient is assigned to the next sequential Patient No. available to the investigator through the Oracle Clinical RDC interface.

The investigator or designated staff will contact the IRT and provide the requested identifying information for the patient to register them into the IRT. Once assigned, the Patient No. must not be reused for any other Patient and the Patient No. for that individual must not be changed. If the patient is randomized but fails to start treatment for any reason, the reason will be entered into the End of Treatment phase Disposition eCRF and IRT must be notified within 2 days that the patient was not treated.

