#### 7.1.1.1 Information to be collected on screening failures

A patient who signed an Informed Consent Form but failed to be started on-treatment for any reason will be considered a screen failure. The screening failure reason will be entered on the Screening Phase Disposition eCRF.

The demographic information, informed consent, and Inclusion/Exclusion pages must also be completed for Screen Failure patients. No other data will be entered into the clinical database for patients who are screen failures, unless the patient experienced a SAE during screening/baseline (see [Section 8](#) for SAE reporting details) or died (Death eCRF should be completed) or withdrew consent (Withdrawal of consent eCRF should be completed).

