### 7.1.2 Treatment period

Patients will be randomized according to a 2:1 ratio, to either the investigational arm or the control arm. An effort should be made to ensure patients start treatment at the latest within 72 hours of randomization.

- **Investigational arm:** PDR001 at the RP2D as established in the [\[CPDR001X2101\]](#) phase I (first-in-human) study (400mg i.v.Q4W).
- **Control arm:** Commonly used chemotherapy as per investigator's choice.

For the purpose of scheduling and evaluations, a treatment cycle will consist of 28 days for patients treated with PDR001. Patients treated with PDR001 who meet the following criteria may continue treatment in additional cycles:

- Patients with a CR, PR or SD will continue to receive PDR001 until confirmed CR or until the patient experiences unacceptable toxicity.
- Patients with PD according to the RECIST v1.1 that has been confirmed but is not worsening and in stable or improved clinical status. These patients should remain under treatment until there is a further progression or clinical deterioration.

Note: Patients treated with PDR001 will **not** be discontinued from the study treatment due to progressive disease as per RECIST v1.1.

Accumulating evidence indicates that objective responses to immunotherapy follows delayed kinetics of weeks or months, and can be preceded by initial apparent radiological progression or appearance of new lesions or some enlarging lesions while other target lesions are regressing (“mixed response”) (Wolchock et al 2009). It is therefore reasonable to allow for these possibilities and continue to treat the patient until progression is confirmed and found to be advancing at the next imaging assessment as per immune-related Response Criteria (irRC). An outline of the irRC is provided in [Appendix 2](#).

Example criteria for continuing treatment beyond progression are below:

- Absence of signs and symptoms (including worsening of laboratory values) indicating disease progression
- No decline in ECOG performance status
- Absence of rapid progression of disease
- Absence of progressive tumor at critical anatomical sites (e.g., cord compression) requiring urgent alternative medical intervention

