### **10.1 Analysis sets**

#### **10.1.1 Full Analysis Set**

The Full Analysis Set (FAS) comprises all patients to whom study treatment has been assigned by randomization. According to the intent to treat principle, patients will be analyzed according to the treatment (and strata) they have been assigned to during the randomization procedure. The FAS will be the primary population for all efficacy related data analyses.

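### The screen-failure definition is not limited to unrandomised patients, so a randomised patient who never starts treatment is both in the Full Analysis Set and excluded from analysis

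*Protocol*

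**What the plan says.** Two protocol sections define a screen failure. Section 10 (Statistical methods and data analysis) says: "Screen failure patients are those who signed the informed consent, but never started the study treatment for any reason". It adds that the eCRF data collected for these patients "will not be included in any analysis, but will be reported in the CSR as separate listings". Section 7.1.1.1 says that a consented patient who "failed to be started on-treatment for any reason will be considered a screen failure", with the reason recorded on the Screening Phase Disposition eCRF. Demography, consent and eligibility pages are completed. Beyond those, "No other data will be entered into the clinical database for patients who are screen failures", except for an SAE during screening, a death or a withdrawal of consent. Neither section adds the condition that the patient was not randomised.

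Other sections treat a randomised patient who is never dosed differently:

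- Protocol Section 10.1.1 defines the FAS, which "comprises all patients to whom study treatment has been assigned by randomization". It invokes the intent-to-treat principle and makes the FAS primary for efficacy. SAP Section 2.2 repeats this.
- Protocol Section 6.4.1 provides that if a patient "is randomized but fails to start treatment for any reason, the reason will be entered into the End of Treatment phase Disposition eCRF", and the IRT is to be told within 2 days.
- SAP Section 5.2, in its date rules for prior anti-neoplastic therapy, substitutes the randomisation date for patients who were randomised but never treated.

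**The concern.** A definition that turns on dosing, and ignores randomisation, captures patients who already have an assigned arm. Read literally, the protocol then gives two answers on whether such a patient is analysed and two answers on which disposition form is used.

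The intent-to-treat population is what is at stake. The trial is open-label, so a patient may decline treatment after learning the allocation, and this need not happen equally in both arms. Removing such patients after randomisation is what an all-randomised analysis set is meant to prevent. The data-entry bar matters separately from the analysis exclusion, because follow-up that is never entered cannot be restored by the FAS definition at the analysis stage.

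**Working it through.** No figure in the plan is in dispute, so there is nothing to reproduce. The check follows one patient through the text: consented, eligible, randomised, never dosed.

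1. **Can this patient exist?** Yes. Section 6.4.2 places randomisation before dosing. Section 7.1.2 gives the interval as a target: "An effort should be made to ensure patients start treatment at the latest within 72 hours of randomization". Section 6.4.1 provides for exactly this patient.

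2. **Is the patient a screen failure?** Under Sections 7.1.1.1 and 10, yes. Consent was signed and treatment never started, and any reason suffices.

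3. **What follows from each rule?**

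| Question | Screen-failure text (Sections 7.1.1.1 and 10) | Text for randomised patients |
|---|---|---|
| Analysed? | No, listings only | Yes, in the FAS under the assigned arm (Section 10.1.1; SAP 2.2) |
| Disposition form | Screening Phase Disposition | End of Treatment phase Disposition (Section 6.4.1) |
| Prior anti-neoplastic therapy data | Not among the pages to be entered | Presupposed by the date rule in SAP 5.2 |
| Later survival contacts | Not entered, although a death is | Survival follow-up covers all patients (Section 7.1.7) |

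4. **Does a narrow reading of Section 10 help?** One could read it as excluding only the eCRF data collected under Section 7.1.1. The conflict remains. Section 10.2 summarises baseline data on the FAS, and Section 7.1.1.1 still stops most other entry for this patient.

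5. **How many patients?** The Amendment 05 study status gives 122 randomised, 82 of them to PDR001, so 122 − 82 = 40 to control. Neither document says how many were never treated. If that number is k, the FAS is 122 by its own definition and 122 − k if the screen-failure rule is applied. The 72-hour target suggests that k is small, but this is an inference.

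6. **What would change?** A non-starter with no post-baseline scan and no death is censored at randomisation (Appendix 1, Sections 14.1.3.2.7 and 14.1.4.5.1, duration 1 day), so leaving that patient out has essentially no effect on the PFS comparison. What could be lost is an early death that should count for PFS or OS, later survival information, and a correct count of the population. If Section 7.1.1.1 were followed instead of Section 6.4.1, the patient would have no End of Treatment page. SAP Section 2.3.1 would then count that patient as still on treatment.

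**The case against.** The best reply is that the specific rules govern the general one. The FAS definition is explicit and rests on intent-to-treat. SAP Section 2.7 runs the secondary efficacy analyses on the FAS, and SAP Section 5.1 anchors the efficacy baseline to randomisation. SAP Section 2.2.1 removes patients from analysis sets through listed deviations, and screen failure is not among the listed grounds. Section 6.4.1 is the specific rule for this patient. Section 7.1.1.1 sits within the screening text, and Section 10 introduces its reporting rules with a proviso for exceptions stated elsewhere.

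Most of this stands as evidence of intent. It does not remove the conflict. How far the proviso in Section 10 reaches is arguable, and Section 6.4.1 covers only the form and the IRT notice. It does not lift the data-entry bar.

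A reader might infer more than the documents support:

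- **That the ORR denominator is left open.** Appendix 1 says that patients with unknown response may be included, but it ties this to the analysis population and gives intent-to-treat populations as its example. SAP Section 2.7 applies the FAS to ORR, and unknown patients are not counted as responders.
- **That missed scans cannot be counted without a first dose.** Appendix 1 falls back on the randomisation date when there is no post-baseline scan, so the schedule can be derived from there.
- **That SAP Table 2-1 removes undosed patients from the FAS.** The FAS and Safety Set rows run together in the available text, so nothing can be concluded from it.
- **That the PFS test is biased by a stated amount.** Any such figure needs a number of non-starters, which is not given.

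**Conclusion.** The contradiction is real and stands in current text. As written, the screen-failure rule would drop randomised patients from an intent-to-treat analysis and send them to a different form from the one that Section 6.4.1 requires. It would be too strong to conclude that the sponsor meant to exclude these patients or did exclude them. The FAS definition, Section 6.4.1 and the SAP date rule all point the other way, and no document reports what was done.

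The point is minor. It rests on the wording alone and assumes no number of affected patients. The practical effect is probably small: few non-starters are likely, deaths are recorded even for screen failures, and PFS and OS are already timed from randomisation. SAP Section 2.2.3 records that the primary efficacy analysis has been reported and was not statistically significant. What remains useful is a consistent population and disclosure of how these patients were handled.

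**What to change.** - In protocol Sections 7.1.1.1 and 10, limit screen failure to patients who consented but were not randomised.
- In Section 7.1.1.1, refer to Section 6.4.1 for patients who were randomised but never treated.
- State in the protocol and SAP that these patients stay in the FAS under their assigned arm, and that their available follow-up and death data are entered and analysed.
- In the CSR, report their number by arm and say whether the PFS analysis already reported included them.

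The cost is close to nil: wording in two protocol sections, a sentence in the SAP (by amendment before database lock or addendum after it, as SAP Section 1 provides) and a check of the affected records. Enrolment is complete, so scans that were never taken cannot be recovered. The SAP sentence and the CSR disclosure are therefore the most useful steps now.

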## **Data analysis after crossover**

For patients who crossover to PDR001 after progression as per RECIST v1.1 to chemotherapy in the control arm, the data will be presented in listings separately from the randomized part of the study. If there are at least 10 patients crossing over, summary tables may be presented with frequency count and percentage for categorical data and descriptive statistics for continuous data. For these patients, the date of their first dose of PDR001 will be used as the starting date to define their safety and efficacy endpoints (such as ORR, irPFS and OS). Details will be provided in the RAP.

